5.1. Sample size calculation

Pilot trials do not require a formal sample size calculation. However, a sample of at least 64 participants per arm is desirable (Teare et al., 2014) for a binary outcome in a pilot trial. We will aim to recruit 6-10 clusters (3-5 sites randomised in each arm) to allow subsequent sample size calculation for a definitive RCT. Within each Talking Therapies site, we will aim to recruit a minimum of 1 therapist that carry out routine assessment (maximum of 2 therapists per site). Each Talking Therapies site will aim to recruit 64 patients, For this, a total of 432 patients would be screened (216 patients per arm). As we expect approximately 30% of patients across sites to have a differential response, we estimate there would need to be 216 patients screened (64 patients per arm; 216*30% = 64). This calculation is based on the assumption of equal availability for treatment. As a pilot trial, any differences in treatment offer and waiting time for the different treatments will be reported and considered for potential subsequent research.

Overall, we will aim to recruit a minimum of 6-10 therapists that carry out routine assessments across the 6-10 Talking Therapies services (1 to 2 per Talking Therapies service). Between the 6 to 20 therapists, we expect that they will assess at least 432 during a 1-year study period, which would require each therapist to assess 1 to 2 cases per week on average.

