Primary outcome(s)	Reliable and Clinically Significant Improvement in depression using a	
	patient-level measure (PHQ-9).	
Randomisation and	Consenting Talking Therapies sites will be randomly assigned to an	
interventions	intervention group labelled 'TherapyMatch-D' or a control group labelled	
	'allocation as usual' (AAU). Consenting therapists of sites in both groups will be trained to use a computer programme called TherapyMatch-D	
	containing an algorithm which will identify consenting patients with a	
	differential treatment response (prior research suggests would be approx.	
	30% of the sample). From that sub-sample, patients in TherapyMatch-D	
	group will be provided a personalised treatment selection recommendation	
	(between CBT and PCE-CfD) based on the targeted prescription algorithm to	
	be used alongside shared decision making. Patients in AAU group will be	
	allocated to treatment as usual (treatment selection based solely on	
	shared-decision making). All patients without an identified differential	
	treatment response across both groups (estimated to be approx. 70%) will	
	also be allocated as usual to treatment (i.e., either CBT or PCE-CfD).	
Planned Sample Size	Pilot trials do not require a formal sample size calculation. However, we will	
	aim to recruit 6-10 clusters (3-5 sites randomised in each arm) with a total of	
	432 patients screened (216 patients per arm). As we expect approximately	
	30% of patients to have a differential response, we estimate there would be	
Data analysis mesthes	128 eligible patients (64 patients per arm).	
Data analysis method	1. Trial data will be summarised using a CONSORT diagram and	
	analyses will be based on intention-to-treat principles.Patient-outcome data will be analysed using multi-level logistic	
	regression. Post-treatment reliable and clinically significant improvement	
	Tregression. Fost-treatment reliable and chincally significant improvement	

	(RCSI) in depression symptoms will be the primary outcome, and will be compared between TherapyMatch-D and AAU. 3. The primary aim will be to examine between-group differences comparing cases using the treatment selection model versus AAU, in the sample of patients where a differential treatment response was identified. 4. Secondary analyses will involve comparing between-group differences in anxiety symptoms, functional impairment, dropout rates, and
	outcome expectancy, and adverse events.

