Patients who are assessed as ineligible for treatment in Talking Therapies (e.g., those who are signposted to other services). Specific criteria for Talking Therapies exclusion is detailed elsewhere (National Collaborating Centre for Mental Health, 2020). Common examples include having other severe mental health disorders, highly acute suicide risk, and comorbid substance use disorder that interferes with the person's ability to engage in therapy.

Note. We will gather information from all consenting participants (216 per arm). However, only those will a differential treatment response as identified by the algorithm in the TherapyMatch-D computer programme, which we estimate would be approximately 30% of the 216 participants (64 participants per arm), will be included in the primary outcome analysis.

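### Section 5.1 gives 64 both as the target per arm and as the target per site; the per-site figure does not fit 432 patients, and the number assessed and the caseload need reconciling with it

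*Protocol*

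**What the plan says.** Protocol section 5.1 starts from the statement that "a sample of at least 64 participants per arm is desirable" for a binary outcome in a pilot. On sites it says "We will aim to recruit 6-10 clusters (3-5 sites randomised in each arm"; on the site target it says "Each Talking Therapies site will aim to recruit 64 patients, For this, a total of 432 patients would be screened", and it splits the 432 into 216 per arm. With about 30% expected to be differential responders, it arrives at 64 per arm. The synopsis agrees at arm level, with 432 screened and "128 eligible patients (64 patients per arm".

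The note at the end of section 4.6 uses the same 216 under another label: "We will gather information from all consenting participants (216 per arm".

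The last paragraph of section 5.1 has the therapists assess no fewer than 432 patients in one year. It sets their number at a minimum of 6 to 10 and then at 6 to 20, and gives the workload as a figure "which would require each therapist to assess 1 to 2 cases per week on average".

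Section 4.8 describes the order of events. The recruitment script is read to every patient assessed by a participating therapist, data go into the programme only after consent, and the programme logs how many are invited, eligible and refuse. No eligibility or consent rate is given.

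**The concern.** The number 64 appears in section 5.1 in two roles that cannot both hold: what each arm should contribute to the primary analysis, and what each site should recruit. An arm is to have 3 to 5 sites, so the two differ by a factor of three to five if they count the same kind of patient. If the per-site figure counts consenting patients instead, it should add up to 432 over the sites.

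This matters in practice because it is the only per-site recruitment target in the protocol, and section 4.8 says that sites are sent the protocol to judge their capacity and capability. A site planning from this sentence plans for the wrong number.

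Two linked figures raise a related question. If 432 is both the number assessed and the number consenting, nothing is allowed for patients who refuse or are ineligible. If the weekly caseload does not follow from 432 and the stated number of therapists, sites cannot use it to judge workload.

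**Working it through.** **Inputs from the protocol.** 64 per arm, 64 per site, 6 to 10 sites, 432 in total (216 per arm), 30% differential responders, 6 to 20 therapists, a 1-year study period, and 1 to 2 cases per therapist per week (section 5.1); 216 per arm consenting (section 4.6); 128 in total (synopsis).

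**Step 1: the plan's own figure.** 216 × 0.30 = 64.8, stated as 64. In total, 432 × 0.30 = 129.6, stated as 128 = 2 × 64. In reverse, 64 / 0.30 = 213.3, so 216 per arm suffices. The arm-level calculation reproduces apart from rounding.

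**Step 2: 64 per site.** The table uses total = 64 × sites; differential responders per arm = total × 0.30 / 2 if the 64 are consenting patients and the arms are equal; patients needed = total / 0.30 if the 64 are differential responders; and average site target = 432 / sites.

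| Sites | 64 × sites | Responders per arm (64 = consenting) | Patients needed (64 = responders) | 432 / sites |
|---|---|---|---|---|
| 6 | 384 | 57.6 | 1,280 | 72.0 |
| 7 | 448 | 67.2 | 1,493 | 61.7 |
| 8 | 512 | 76.8 | 1,707 | 54.0 |
| 9 | 576 | 86.4 | 1,920 | 48.0 |
| 10 | 640 | 96.0 | 2,133 | 43.2 |

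No row gives 432, since 432 / 64 = 6.75 sites. Under the consenting reading, 6 sites fall 10% short of 64 per arm (57.6 / 64 = 0.90) and 10 sites exceed it by 50% (96 / 64 = 1.50). With an odd number of sites the arms cannot have equal numbers of sites, so 67.2 and 86.4 are averages over the two arms. Under the responder reading, each arm would have 192 to 320 (32 × sites), three to five times the stated 64.

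**Step 3: assessed and consenting.** Let r be the share of assessed patients who are eligible and consent. To obtain 432 consenting, 432 / r must be assessed. If only 432 are assessed, the responders per arm are 432 × r × 0.30 / 2. The protocol gives no r, so 50% to 90% is an assumption.

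| Assumed r | Assessed for 432 consenting | Responders per arm if only 432 assessed |
|---|---|---|
| 90% | 480 | 58.3 |
| 70% | 617 | 45.4 |
| 50% | 864 | 32.4 |

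Only r = 100% makes the two uses of 432 agree (64.8 per arm).

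**Step 4: caseload.** 432 / 52 = 8.31 patients per week. Per therapist this is 1.38 with 6, 1.04 with 8, 0.92 with 9, 0.83 with 10 and 0.42 with 20. The lower bound of 1 per week is met with 8 therapists or fewer. Reaching 2 per week would take 8.31 / 2 = 4.2 therapists, fewer than the stated minimum of 6.

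If 432 / r are assessed over 52 weeks, the weekly load per therapist is:

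| Assumed r | 6 therapists | 10 therapists | 20 therapists |
|---|---|---|---|
| 90% | 1.54 | 0.92 | 0.46 |
| 70% | 1.98 | 1.19 | 0.59 |
| 50% | 2.77 | 1.66 | 0.83 |

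Even at r = 50%, 20 therapists do not reach 1 per week, while 6 therapists exceed 2.

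**The case against.** The strongest reply is that this is one wrong word. The synopsis, section 4.6 and the rest of section 5.1 all give 64 per arm, and the per-site sentence is followed at once by the correct total and its split by arm. It probably should have said arm. That is plausible, though the text does not prove it, and no other part of the protocol corrects the site target. The inconsistency stands; its size should not be exaggerated.

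A reader might infer that the per-site target makes the trial under-recruit. The protocol does not support that. The total falls short only at 6 sites and overshoots from 7 sites up, and an aim is not a stopping rule.

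A reader might also see a contradiction between screened and consenting. There need be none: data are entered only after consent, so the patients screened by the algorithm can be the consenting ones. What remains is the conflict with the number assessed. The protocol states that number as a floor, which allows more to be assessed, but it gives no rate linking assessed to consenting.

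On caseload, 52 weeks ignores leave. With an assumed 42 to 46 working weeks, 6 to 10 therapists would see about 0.94 to 1.71 patients per week, close to the stated range. Twenty would still see only 0.47 to 0.51, so the mismatch at the upper staffing end stands.

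Finally, a reader might argue that 64 per arm is too small once clustering is counted. The protocol gives no basis for calling this an error. It disclaims a formal sample size calculation, plans no hypothesis testing (section 3.3), makes no precision claim for 64 per arm, and models therapist and site levels in section 5.2 while admitting that those random effects will probably be estimated unreliably.

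**Conclusion.** The point holds as an inconsistent recruitment target, not as a failure of the sample size. The per-site 64 agrees with neither 432 patients nor 128 differential responders at any planned site count. As consenting patients it gives 384 to 640 in total and about 58 to 96 responders per arm; as responders it implies 1,280 to 2,133 patients. The step from 216 per arm to about 64 is correct.

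Two smaller faults go with it. The same 432 serves as the number assessed and the number consenting, which agrees only if nobody refuses or is ineligible, although the protocol logs both. The stated caseload holds for 6 to 8 therapists over 52 weeks (1.38 to 1.04 per week) but not across the 6 to 20 named in the same sentence.

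The per-arm results assume equal arms and the protocol's 30%. The 50% to 90% eligibility-and-consent range is an assumption, as is a 52-week year.

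**What to change.** - In section 5.1, replace the per-site 64 with 64 differential responders per arm. Set the site target as 432 divided by the number of sites: on average 72 consenting patients with 6 sites and about 44 with 10 (43.2 rounded up), if sites are of equal size.
- Use consenting for the 432 (216 per arm) in the synopsis, section 4.6 and section 5.1.
- Give the larger number to be assessed separately, under a stated range for the eligibility-and-consent rate; for example 480 to 864 at an assumed 90% to 50%.
- Recompute the weekly assessments per therapist from that larger number across 6 to 20 therapists, and state the number of weeks used. The figure should remain one for patients assessed, because a figure for consenting patients alone would understate the work.

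The cost is rewording of the synopsis, sections 4.6 and 5.1, and whatever site targets were taken from them. The stated assessment workload becomes larger. The planned consenting sample does not increase.

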5.2. Primary analysis

Patient-level clinical outcome data will be analysed using logistic multilevel modelling conducted according to the intention-to-treat principle according to CONSORT guidelines for Cluster RCTs. Researchers will be blinded to the group allocation while analysing the trial data.

The primary outcome will be defined as reliable and clinically significant improvement (RCSI) in depression symptoms (PHQ-9) after treatment, based on the method described by Jacobson and Truax (1991). A 3-level model will be applied, with patients nested within therapists, nested within Talking Therapies sites, and post-treatment RCSI in depression (PHQ-9) symptoms as the dependent variable. Group (TherapyMatch-D vs. usual care) will be entered as a level-2 predictor, along with baseline PHQ-9 as a level-one covariate. This method will enable us to determine whether TherapyMatch-D is associated with a greater treatment effect (depression symptom reduction) by comparison to usual care and will be specifically run in the target sample of patients identified as having a differential response to treatment. The three-level model will account for the nested structure of the data, as appropriate within a cluster trial design. Given the small sample sizes of this pilot trial, it is unlikely the estimates of random effects for site and therapist will be reliable, but this data may be used to guide subsequent research. If the site and therapist random intercepts are not statistically significant, a one-level parsimonious multivariate regression model will be estimated as a sensitivity analysis. Adjusted odds ratios and confidence intervals will be reported as a primary effect sizes. In addition, we will also report the results in the best fitting model following analyses of goodness of fit to find the most parsimonious model.

We acknowledge that some patients might decide to switch from one therapy to another following allocation in either arm of the trial (i.e., patient allocated to CBT after consenting to treatment asks to switch to PCE-CfD), as occurs in routine practice occasionally. In this pilot trial, we will report the frequency of this occurrence and circumstances. Cases will be included in the primary analysis (as part of the

allocation group to which they were originally allocated to), and secondary analyses will exclude these cases to examine the extent to which this data might contaminate the results. The same reporting and inclusion of cases for primary analyses will be followed in cases where patients and clinicians select another High Intensity Treatment beyond the two examined in this trial.

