4.7 Primary and Secondary Outcomes and Measures

Primary outcome and measure

This study aims to pilot effectiveness of using a targeted prescription to guide treatment selection to improve clinical outcomes in depression relative to AAU, for which the main outcome variable is RCSI in depression. Effectiveness will be measured by the Patient Health Questionnaire-9 (PHQ-9) at the end of the treatment period (last session of CBT or PCE-CfD), with adjustment for baseline depression.

The PHQ-9 (Kroenke et al., 2001) is a brief measure commonly used to monitor the severity of depression and response to treatment. Each of the nine items is scored on a 0-3 scale. Item scores are summed to give an overall severity rating (range 0-27). The PHQ-9 has been validated for use in primary care (Kroenke et al.,2010), with adequate sensitivity (88%) and specificity (88%) estimates for the detection of major depressive disorder using a cut-off score ≥ 10 . RCSI was determined based on the method described by Jacobson and Truax (1991), by combining reliable change index (PHQ ≥ 6) and diagnostic cut-offs (PHQ-9 < 10).

Secondary outcomes and measures

The secondary outcome measures aimed to measure feasibility (adherence to the recommendation provided by the targeted prescription algorithm and outcome expectancy) and effects (anxiety, functional impairment, drop-out rates and adverse events). The specific variables were chosen as additional ways to measure improvement in clinical outcomes, to control for complexity and those variables that were identified to predict a differential response to treatment in the development of the targeted prescription

algorithm, and therefore needed to provide a targeted prescription recommendation of treatment (Delgadillo & Gonzalez Salas Duhne, 2020).

The specific measures for the secondary outcomes are:

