4.3. Secondary analyses

The above modelling strategy will be repeated to compare the rate of improvement (RCSI) in GAD-7 anxiety symptoms, and RCSI in depression symptoms only in the cases who attended at least one treatment session. We will also compare outcome expectancy, dropout rates and adverse effects between groups, and compare characteristics between those who attended at least one treatment session versus those who dropped out following assessment. For both TherapyMatch-D and control groups, we will estimate the proportions of participants who had RCSI post-treatment, and who completed/dropped out of treatment. We will also calculate and report effect sizes for each of the symptom measures (PHQ-9, GAD-7, WSAS) using Cohen's *d* metric (Cohen, 1988), based on mean differences between groups. Treatment attendance, completion, and dropout rates will be presented diagrammatically and based on CONSORT guidelines. To quantify any potential adverse effects related to the trial, we will also calculate a rate of reliable deterioration in patients across both arms of the trial. Further, we will use the data collected to identify complex cases (see StratCare Trial from Delgadillo et al., 2021) and control for variability in complex cases across Talking Therapies sites.

We will examine adherence to the TherapyMatch-D model using the full study sample of participants with a differential treatment response across both arms. Each therapist's Treatment-Matching Precision Score (TMaP) will be calculated, which is a statistical measure of agreement between their observed treatment selection and the recommendations made using the prognostic algorithm. In the experimental group, this would represent the agreement of patients accepting the recommended treatment. In the control group, this is the post-hoc analysis of the agreement the optimal treatment that the prescriptive algorithm would recommend (which patients did not receive, since they were in the control group) and the actual treatment selected via shared decision making. A comparison of mean TMaP scores between groups will be done using parametric or non-parametric tests, depending on the distribution of TMaP scores.

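### Every planned depression model uses yes/no RCSI, although section 5.2 says it shows symptom reduction; a baseline-adjusted multilevel model of the PHQ-9 score should sit beside it

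*Protocol*

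**What the plan says.** Protocol section 4.7 describes the PHQ-9 as a summed score: "Item scores are summed to give an overall severity rating (range 0-27"). It says effectiveness is measured by this scale at the last session with adjustment for baseline, "for which the main outcome variable is RCSI in depression". RCSI requires a change of at least 6 points and a final score below 10.

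Section 5.2 specifies a three-level logistic model with "post-treatment RCSI in depression (PHQ-9) symptoms as the dependent variable", arm as predictor, "along with baseline PHQ-9 as a level-one covariate". On reporting, it states: "Adjusted odds ratios and confidence intervals will be reported as a primary effect sizes". The one-level sensitivity model and the best-fitting model in that section concern the same outcome. The same paragraph says the method will show whether the intervention gives a "greater treatment effect (depression symptom reduction) by comparison to usual care".

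The secondary analyses section (numbered 4.3, but placed under section 5) continues: "The above modelling strategy will be repeated to compare the rate of improvement (RCSI) in GAD-7 anxiety symptoms". It also repeats the strategy for depression RCSI among patients who attended at least one session. For the scores themselves (PHQ-9, GAD-7, WSAS) it plans only Cohen's d, based on mean differences between groups.

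Section 3.3 plans no hypothesis testing. Section 5.1 takes 64 per arm from a recommendation for a binary outcome in a pilot trial, and recruits 6-10 clusters to inform the sample size of a definitive trial.

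**The concern.** There are two linked problems.

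First, the stated purpose and the model do not match. An RCSI odds ratio describes how often patients meet a rule, not how far symptoms fall. A patient who goes from 24 to 11 has improved by 13 points but does not meet the rule, and is coded the same as a patient with no change. Section 5.2 nevertheless presents the model as answering a question about symptom reduction.

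Second, the score is recorded at assessment and at every session, but no planned regression uses it as an outcome. The planned d has no stated baseline adjustment, clustering or interval. With about 64 analysed patients per arm in 6-10 sites, intervals will already be wide, and cutting the score widens them further. It also means that no planned model gives the definitive trial a score-scale residual SD, baseline correlation or site ICC.

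**Working it through.** **Inputs from the protocol.** 216 screened per arm, 30% differential responders, 64 analysed per arm and 128 in total (synopsis, 5.1). 6-10 sites (5.1). RCSI rule and 0-27 scale (4.7). Recovery of about 50% (section 2), used here as a stand-in for the RCSI rate and varied. The protocol gives no ICC, PHQ-9 SD or pre-post correlation, so every value for these below is an assumption.

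**1. The plan's own figure.** 216 × 0.30 = 64.8, stated as 64 per arm. 432 × 0.30 = 129.6, stated as 128. Both reproduce to within rounding.

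**2. Patient-level loss.** For a normal outcome cut so that a proportion p respond, the efficiency of the binary analysis relative to the score is φ(z_p)² / [p(1 − p)].

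- p = 0.50: 0.3989² / 0.25 = 0.637, loss 36%
- p = 0.40 or 0.60: 0.622, loss 38%
- p = 0.35 or 0.65: 0.603, loss 40%

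The interval, relative to the effect, is wider by 1/√0.637 = 1.25 to 1/√0.603 = 1.29, that is 25-29%. For independent patients, 128 analysed as RCSI carry the information of 128 × 0.637 ≈ 82 down to 128 × 0.603 ≈ 77 analysed on the score.

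**3. The actual RCSI rule.** RCSI is not one fixed cut: from a baseline of 15 or more a final score of 9 suffices, but from a baseline of 10 the score must fall to 4. The rule was therefore simulated (400,000 patients per setting). Assumptions: baseline rounded normal, mean 16, SD 5, kept within 10-27; end score SD 6.3, rounded and clipped to 0-27; pre-post correlation 0.3-0.6; control RCSI rates about 30-50%; a 1.5-point arm difference. Baseline-adjusted logistic regression lost 36-46% against ANCOVA, still without clustering.

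**4. Allowing for clustering.** The ICC of a dichotomised outcome is smaller than that of the underlying score, so clustering penalises the score analysis more and narrows the gap. With m = 128/k patients per site:

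RE = {φ(z_p)² / [p(1 − p)]} × [1 + (m − 1)ICC] / [1 + (m − 1)ICC_bin]

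- Smallest loss: p = 0.5, ICC 0.10 (ICC_bin 0.0638), 6 sites, m = 21.3. 0.637 × 3.03 / 2.30 = 0.84, loss 16%.
- Largest loss: p = 0.4, ICC 0.01 (ICC_bin 0.0062), 10 sites, m = 12.8. 0.622 × 1.118 / 1.073 = 0.648, loss 35%.

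| Assumed latent ICC | Loss, 6-10 sites, RCSI rate 40-50% |
|---|---|
| 0.01 | 32-35% |
| 0.02 | 29-33% |
| 0.05 | 22-28% |
| 0.10 | 16-22% |

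The corresponding extra interval width runs from 1/√0.841 = 1.09 to 1/√0.648 = 1.24, that is 9-24%. This step uses one level of clustering (site) and equal site sizes.

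**5. What the planned outputs deliver on the score scale.** The d gives a standardised difference in group means. No stated output gives a baseline-adjusted difference that respects sites and therapists, and no planned model gives a score-scale ICC.

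**The case against.** The strongest case against is that RCSI was chosen deliberately and coherently. It is fully defined, the earlier algorithm study reported its result on it, and 64 per arm was taken from a recommendation for a binary outcome. A supportive linear model might also be in a statistical analysis plan that is not shown. A score-scale contrast is already planned through Cohen's d, and section 5.2 names RCSI and odds ratios so plainly that few readers would mistake what is estimated.

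Much of this stands. RCSI is a legitimate primary outcome and nothing here argues for replacing it. The possible content of an unseen plan is a fair caution, but the protocol itself fixes the dependent variable, the model, the effect measure and the basis of d, and its phrase about symptom reduction is wrong for that model whatever another document says.

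Three stronger readings are tempting, and the documents do not support them.

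- *The trial is underpowered because of the cut.* With 50% against 70% RCSI (odds 1 × 2.33 = 2.33; 2.33/3.33 = 0.70) and 64 per arm, power ignoring clustering would be about 64% for RCSI and 84% for the score. But section 3.3 plans no testing and section 5.1 makes no power claim. The OR of 2.33 in section 2 compares patients given their optimal therapy with those given the suboptimal one, not the trial arms.
- *The trial throws away 35-40% of its 128 patients.* That is a patient-level figure, and in this cluster design the loss is probably smaller.
- *A score endpoint could not be planned from this pilot.* Group means and SDs are needed for the planned d, and a pre-post correlation is a simple summary of data already held. Only the site ICC truly needs a model, and section 5.2 already concedes that random-effect estimates are unlikely to be reliable at this size.

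**Conclusion.** The point holds as a cheap improvement and a wording correction. It is not a fault in the primary endpoint or the sample size. The mismatch between an RCSI odds ratio and the claim about symptom reduction follows from the text alone and needs no assumption. The loss of information is about 36-40% at patient level for RCSI rates of 35-65%, and about 16-35% with clustering at rates of 40-50%. The second range depends on assumed ICCs of 0.10 to 0.01 and an approximately normal underlying score. The consequence is less precision, and planning inputs for the definitive trial that rest on a d with no stated adjustment.

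**What to change.** - In section 5.2, keep RCSI as the primary outcome and describe its model as estimating the odds of RCSI. Remove the statement that it determines symptom reduction.
- In section 5.2 and the secondary analyses, pre-specify a supportive linear multilevel model of end-of-treatment PHQ-9 with arm, baseline PHQ-9 and the same site and therapist structure. Do the same for GAD-7 with its own baseline.
- Report the adjusted mean difference with 95% CI, the residual SD, the baseline correlation and the site ICC, noting that the ICC will be imprecise with 6-10 sites.
- Base the standardised effect size for these two measures on the adjusted difference.

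The cost is one extra model per measure on data already collected, with no new patients, visits or instruments and no change to the sample size. The small downside is a second effect estimate to report, on a bounded score whose residuals are only approximately normal. As no hypothesis testing is planned, it carries no multiplicity penalty.
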